4.2 Study Endpoints**4.2.1 Primary Study Endpoints**

The primary study endpoints will be length of hospital stay expressed in days and the time on supplemental oxygen support expressed in days, and these endpoints will be compared between the control and experimental group.

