10.2 Statistical Hypotheses

The statistical hypotheses are as follows:

- Null hypothesis: combined nebulized hypertonic saline nebulization with chest percussion therapy in patients age 0 to 24 months admitted to the general inpatient pediatrics unit with acute bronchiolitis will not have any significant effects on primary outcomes (length of stay and number of days on supplemental oxygen therapy) and secondary outcomes (objective clinical responses included respiratory rate, heart rate, and oxygen saturation and subjective clinical responses from physicians and caregivers).
- Alternative hypotheses: combined nebulized hypertonic saline nebulization with chest percussion therapy in patients age 0 to 24 months admitted to the general inpatient pediatrics unit with acute bronchiolitis will have clinically significant effects on primary outcomes (length of stay and number of days on supplemental oxygen therapy) and secondary outcomes (objective clinical responses included respiratory rate, heart rate, and oxygen saturation and subjective clinical responses from physicians and caregivers).

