10.4.2 Analysis of the Primary Efficacy Endpoint(s)

For all analyses, the standard assumptions of Gaussian residuals and quality of variance will be tested. If the standard assumptions are not met, a transformation will be performed (i.e. logarithm transformation). Results will be brought back to the original units and reported as geometric means with their corresponding lower and upper confidence limits.

For the assessment of number of days on supplemental oxygen therapy (i.e. count data), a Poisson, Negative Binomial (NB), Zero-Inflated Poisson (ZIP), or Zero-Inflated Negative Binomial (ZINB) model will be used.

A result will be considered statistically significant at the $p < 0.05$ level of significance. All analyses will be performed using SAS version 9.4 (SAS Institute Inc., Cary, NC).

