10.5 Sample Size

The proposed sample size for this study is 228 subjects ($n=114$ per group). Based on data published by Gajdos, et al., the mean duration of hospitalization for bronchiolitis recorded in the study hospitals during previous years was 6.5 days and standard deviation = 3.5 days. For a type I error of 0.05 and a power of 0.80, for detecting a 20% decrease in duration of hospitalization, a total of 228 subjects would be included (114 subjects in each group).

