10.6 Measures to Minimize Bias

This study is not blinded. All patients who meet the inclusion criteria are eligible to enroll in the study and would be receiving the investigational therapy of nebulized 3% hypertonic saline combined with chest percussion therapy. These participants will be part of the experimental arm of the study. No masking or randomization is required. It is expected that at least 114 subjects in this group will be required to accommodate for a type I error of 0.05 and a power of 0.80. An estimate of approximately 200 participants will be required to be enrolled in this study to account for early withdrawal from the study for any reason.

11 Source Documents and Access to Source Data/Documents

Source data is all information, original records of clinical findings, observations, or other activities in a clinical trial necessary for the reconstruction and evaluation of the trial. Source data are contained in source documents. Examples of these original documents, and data records include: hospital records, clinical and office charts, laboratory notes, memoranda, subjects' diaries or evaluation checklists, pharmacy dispensing records, recorded data from automated instruments, copies or transcriptions certified after verification as being accurate and complete, microfiches, photographic negatives, microfilm or magnetic media, x-rays, subject files, and records kept at the pharmacy, at the laboratories, and at medico-technical departments involved in the clinical trial. It is acceptable to use CRFs as source documents. If this is the case, it should be stated in this section what data will be collected on CRFs and what data will be collected from other sources.

The study case report form (CRF) is the primary data collection instrument for the study. All data requested on the CRF must be recorded. All missing data must be explained. If a space on the CRF is left blank because the

procedure was not done or the question was not asked, write "N/D". If the item is not applicable to the individual case, write "N/A". All entries should be printed legibly in black ink. If any entry error has been made, to correct such an error, draw a single straight line through the incorrect entry and enter the correct data above it. All such changes must be initialed and dated. DO NOT ERASE OR WHITE OUT ERRORS. For clarification of illegible or uncertain entries, print the clarification above the item, then initial and date it.

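### Two primary endpoints are each tested at p < 0.05 with no rule on whether one or both must succeed; if either counts, the error across the pair exceeds 5%

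*Combined protocol and SAP*

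**What the plan says.** The Protocol Summary, 3.1, 4.2.1 and 10.2 all name length of stay and oxygen time as primary, and none ranks one above the other. Section 4.2.1 reads: "The primary study endpoints will be length of hospital stay expressed in days and the time on supplemental oxygen support expressed in days".

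Section 10.4.2 sets the threshold: "A result will be considered statistically significant at the $p < 0.05$ level of significance". The same sentence appears in the Protocol Summary, 4.1, 10.4.3 (secondary endpoints) and 10.4.7.2.

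Section 10.2 has one compound null and one compound alternative. The alternative is that treatment "will have clinically significant effects on primary outcomes (length of stay and number of days on supplemental oxygen therapy) and secondary outcomes".

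Section 10.5 plans the sample size on one endpoint: "For a type I error of 0.05 and a power of 0.80, for detecting a 20% decrease in duration of hospitalization". The length-of-stay inputs are a mean for "previous years was 6.5 days and standard deviation = 3.5 days". No mean, SD, effect or power is given for oxygen time, although 10.4.2 assigns it its own family of count models.

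No section gives a hierarchy, an alpha split or a both-must-succeed rule. The table of contents lists a multiplicity section with a broken page reference. The body has none, and runs from 10.4.7 and its subsections straight to 10.4.8 on tabulation.

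**The concern.** With two primaries, one threshold applied to each and no success rule, a reader of the results could call the study positive on length of stay alone, on oxygen time alone, or only on both. These are three different claims with different error rates and different power.

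The choice could also be made late. The study is open-label, control outcomes already exist in charts, and section 1 says that no biostatistician is yet assigned and that analysis waits for one. If the decisive endpoint is picked after results are visible, the more favourable one can carry the conclusion at more than the nominal 5%.

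**Working it through.** **Inputs.** From 10.5: control mean 6.5 days, SD 3.5 days, 20% decrease, type I error 0.05, power 0.80, 114 per group. From 10.4.2: each result judged at p < 0.05. Assumed here because the documents are silent: a two-sided test, and the correlation r between the two test statistics.

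**1. The plan's own figure.** The difference is 0.20 × 6.5 = 1.3 days.

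n per group = 2 × (1.960 + 0.842)² × 3.5² / 1.3² = 113.8, rounded up to 114, or 228 in total. This matches 10.5.

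Power at 114 per group: 1.3 / (3.5 × √(2/114)) = 2.804, and Φ(2.804 − 1.960) = 80.1% (79.7% by the t distribution). A one-sided 0.05 would need only 90 per group. So the stated figure is two-sided and spends the whole 0.05 on length of stay.

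**2. If either endpoint counts.** With no true effect on either endpoint, the chance of at least one significant result is 1 − P(|Z₁| < 1.96 and |Z₂| < 1.96), where Z₁ and Z₂ are standard bivariate normal with correlation r. At r = 0 this is 1 − 0.95² = 9.75%.

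| Assumed r | Error across the two primaries |
|---|---|
| 0 | 9.75% |
| 0.3 | 9.5% |
| 0.5 | 9.1% |
| 0.7 | 8.3% |
| 0.8 | 7.8% |
| 0.9 | 7.0% |
| 0.95 | 6.5% |

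It is above 5% at every r below 1. Whatever the dependence, it cannot exceed 0.05 + 0.05 = 10%.

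**3. If both must succeed.** A false claim needs the endpoint without an effect to reach p < 0.05, so the error is at most 5% with no adjustment. Joint power cannot exceed the lower of the two powers. It is therefore at most 80.1%, and its actual value cannot be computed without oxygen-time inputs.

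**4. Power for oxygen time.** It cannot be derived from the documents. As an illustration only, a 20% decrease with 114 per group under a normal approximation gives 86%, 58% or 33% power at assumed SD-to-mean ratios of 0.5, 0.7 or 1.0. The ratio for length of stay is 3.5/6.5 = 0.54.

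**5. What the repairs cost.**
- *Alpha split, 0.025 each:* at 114 per group, power for length of stay is Φ(2.804 − 2.241) = 71.3% (70.8% by t). Restoring 80% needs 2 × (2.241 + 0.842)² × 3.5² / 1.3² = 137.8, so 138 per group or 276 in total.
- *Fixed sequence, length of stay first at 0.05:* 114 per group and 80.1% power are unchanged. If length of stay has no true effect, any false claim must first pass its 5% test. If it has one, oxygen time is the only possible false claim and is also tested at 5%. The error across the pair is at most 5%.

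**The case against.** The strongest reply is that 10.5 attaches its 0.05 to length of stay only, and for that single test it is right. A reader might infer that the plan's stated type I error is wrong. The documents do not support that: they state no error rate across endpoints, and the sample-size arithmetic reproduces. This part of the reply stands.

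A second reply is that the Protocol Summary's hypothesis and the alternative in 10.2 both join the endpoints with *and*. If both were required, 0.05 would hold. But these are statements of hypothesis, and neither says what counts as success. The null in 10.2, of no significant effects on the listed outcomes, fits an either-endpoint reading at least as well. The inflation is therefore conditional, and the missing rule is the defect.

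Third, the endpoints are probably positively correlated, since time on oxygen in hospital is part of the stay. That makes 9.75% the least plausible figure in the table and favours the lower rows. It reduces the excess without removing it.

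Fourth, 5.5 calls this a pilot and 10.1 refers to a formal SAP. The plan still states hypotheses, a type I error and 80% power, and the combined document contains no rule.

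Finally, in an open, non-randomized comparison with earlier patients, an excess of roughly 1.5 to 5 percentage points may matter less than confounding between periods. That is fair, and it limits the weight of this point.

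**Conclusion.** The point holds in conditional form. The plan has two unranked primaries, an undivided p < 0.05 for each, and no success rule. If either endpoint suffices, the error across the pair is 9.75% under independence and between 9.1% and 6.5% at assumed correlations of 0.5 to 0.95. If both are required, it is at most 5% and the 80% becomes an upper limit on power. The figures assume that each test holds its own 5% level. They say nothing about bias from the historical control.

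Two further inferences should be resisted:
- Powering only length of stay does not raise the type I error. It is a separate gap that leaves the power for oxygen time unknown.
- One could count all seven outcomes in 10.2 and report 1 − 0.95⁷ = 30%. That pools secondary outcomes with the primary family, on which study-level error is normally judged, and it assumes independence. The documents do not make success depend on any one of the seven.

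**What to change.** In the Protocol Summary, 3.1, 4.2.1, 10.2 and 10.4.2, make length of stay the single primary endpoint, or the first in a fixed sequence, because it is the endpoint that 10.5 powers. Test oxygen time at two-sided 0.05 only if length of stay is significant. In 10.2, give each tested endpoint its own null and alternative.

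Limit the blanket p < 0.05 sentence in the Protocol Summary, 4.1, 10.4.2, 10.4.3 and 10.4.7.2 to this sequence; otherwise those sections will contradict the new rule. Report the other secondary outcomes with 95% confidence intervals, as supportive.

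The sample size stays at 114 per group and power for length of stay at about 80%. An alpha split or a both-must-succeed rule would also be coherent. The split lowers length-of-stay power to about 71% at the current size, and requiring both leaves joint power unknown.

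The cost is a protocol amendment, which 13.2 requires the IRB to approve before it is implemented, and the loss of any formal claim on oxygen time if length of stay is not significant. The change should be made before any outcome data are compared.

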4.2.2 Secondary Study Endpoints

The secondary study endpoints will be clinical variables including respiratory rate, heart rate, and pulse oximetry reading and these endpoints will be compared between the control and experimental group. Other secondary study endpoints will be subjective clinical impressions based on caregiver and physician report, and these endpoints will be compared between the control and experimental group. A cost-benefit analysis may also be a potential secondary study endpoint. Because data collected from surveys will reflect the pediatric patients enrolled in the study only, the parents/caregivers and physicians who answer the surveys are not considered research subjects.

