SAE	Serious Adverse Event/Serious Adverse Experience
SOP	Standard Operating Procedure
US	United States

Protocol Summary

Title	Efficacy of combined nebulized hypertonic saline and chest percussion therapy in acute viral bronchiolitis
Short Title	Combined nebulized hypertonic saline and chest percussion in pediatric bronchiolitis
Brief Summary	This study will examine the efficacy of combined nebulized hypertonic saline with chest percussion therapy in patients age 0 to 24 months admitted to the general inpatient pediatrics unit with acute bronchiolitis. 3% nebulized hypertonic saline treatments combined with 3 minutes of chest percussion therapy will be administered every 6 hours of patients selected for the study.
Phase	N/A
Objectives	Primary outcomes measured will be length of hospital stay and time on supplemental oxygen support, both to be measured in hours. The hypothesis will be that combined nebulized hypertonic saline and chest percussion therapy will decrease length of hospital stay and time on supplemental oxygen support. Secondary outcomes measured will be clinical response (respiratory rate, heart rate, pulse oximetry reading), subjective perceptions of caregivers and health care team, and cost-benefit.
Methodology	Cross-sectional quasi-experimental, open, non-randomized clinical study
Endpoint	Primary endpoints include length of hospital stay and time on supplemental oxygen therapy. Secondary endpoints include trend of respiratory rate, heart rate, and pulse oximetry reading following treatments and subjective perceptions of patients' clinical status based on caregiver and health care team.
Study Duration	12 months
Participant Duration	The duration of participation will begin from time of admission to the general inpatient pediatrics unit until time of discharge from the general inpatient pediatrics unit. This duration may vary from patient to patient, on average will last approximately 1-5 days.
Duration of IP administration	The duration of product administration will begin from time of admission to the general inpatient pediatrics unit until time of discontinuation of supplemental oxygen therapy. This duration may vary from patient to patient, on average will last approximately 1-5 days.
Population	Pediatric patients age 0 to 24 months admitted to the general pediatrics unit admitted for acute bronchiolitis requiring supplemental oxygen therapy
Study Sites	NYU Langone Hospital – Long Island, general inpatient pediatrics unit (NP5)

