4.1 Description of Study Design

Groups:

1. Control group: Patients meeting criteria as above prior to start date, beginning 12 months prior to start date of study, will be examined via retrospective chart review

2. Experimental group: All patients meeting criteria as above beginning start date of study will be enrolled in study to receive adjuvant therapy with 3% hypertonic saline nebulization treatments combined with 3 minutes of chest physiotherapy.

Statistical Methods:

Descriptive statistics (mean \pm standard deviation or median [25th, 75th percentiles] for continuous variables; frequencies and percentages for categorical variables) will be calculated separately by group. The two groups will be compared using the chi-square test or Fisher's exact test, as deemed appropriate, for categorical variables and the two-sample t-test or Mann-Whitney test for continuous data.

For all analyses, the standard assumptions of Gaussian residuals and quality of variance will be tested. If the standard assumptions are not met, a transformation will be performed (i.e. logarithm transformation). Results will be brought back to the original units and reported as geometric means with their corresponding lower and upper confidence limits.

For the assessment of number of days on supplemental oxygen therapy (i.e. count data), a Poisson, Negative Binomial (NB), Zero-Inflated Poisson (ZIP), or Zero-Inflated Negative Binomial (ZINB) model will be used.

A result will be considered statistically significant at the $p < 0.05$ level of significance. All analyses will be performed using SAS version 9.4 (SAS Institute Inc., Cary, NC).

Sample Size Considerations:

The proposed sample size for this study is 228 subjects ($n=114$ per group). Based on data published by Gajdos, et al., the mean duration of hospitalization for bronchiolitis recorded in the study hospitals during previous years was 6.5 days and standard deviation = 3.5 days. For a type I error of 0.05 and a power of 0.80, for detecting a 20% decrease in duration of hospitalization, a total of 228 subjects would be included (114 subjects in each group).

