4.2.3 Exploratory Endpoints

There are no exploratory endpoints in this study.

5 Study Enrollment and Withdrawal**5.1 Inclusion Criteria**

In order to be eligible to participate in this study (experimental arm), an individual must meet all of the following criteria:

1. Age 0 to 24 months
2. Admitted to the general inpatient pediatrics unit
3. Has a diagnosis of acute bronchiolitis
4. Receiving supplemental oxygen support

Data collected for the control arm will be obtained via retrospective chart review for patients meeting the following inclusion criteria:

1. Age 0 to 24 months
2. Admitted to the general inpatient pediatrics unit

3. Has a diagnosis of acute bronchiolitis
4. Receiving supplemental oxygen support

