10.4 Description of Statistical Methods

10.4.1 General Approach

Descriptive statistics (mean \pm standard deviation or median [25th, 75th percentiles] for continuous variables; frequencies and percentages for categorical variables) will be calculated separately by group. The two groups will be compared using the chi-square test or Fisher's exact test, as deemed appropriate, for categorical variables and the two-sample t-test or Mann-Whitney test for continuous data.

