10.4.3 Analysis of the Secondary Endpoint(s)

For all analyses, the standard assumptions of Gaussian residuals and quality of variance will be tested. If the standard assumptions are not met, a transformation will be performed (i.e. logarithm transformation). Results will be brought back to the original units and reported as geometric means with their corresponding lower and upper confidence limits.

For the assessment of number of days on supplemental oxygen therapy (i.e. count data), a Poisson, Negative Binomial (NB), Zero-Inflated Poisson (ZIP), or Zero-Inflated Negative Binomial (ZINB) model will be used.

A result will be considered statistically significant at the $p < 0.05$ level of significance. All analyses will be performed using SAS version 9.4 (SAS Institute Inc., Cary, NC).

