10.4.6 Baseline Descriptive Statistics

Baseline descriptive statistics will include participant age and gender.

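### Heart rate and respiratory rate at ages 0 to 24 months are compared across two non-randomised periods with no covariate, although age is known in both arms

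*Combined protocol and SAP*

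**What the plan says.** Section 4.2.2 states: "The secondary study endpoints will be clinical variables including respiratory rate, heart rate, and pulse oximetry reading and these endpoints will be compared". The contrast is treated children against controls. The Protocol Summary words the endpoint differently: "Secondary endpoints include trend of respiratory rate, heart rate, and pulse oximetry reading following treatments".

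The groups come from different periods. Under section 4.1, controls are eligible children admitted before the study, "beginning 12 months prior to start date of study, will be examined via retrospective chart review", and treated children are enrolled from the start date. Section 10.6 adds: "No masking or randomization is required".

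For the comparison, section 10.4.1 names "the two-sample t-test or Mann-Whitney test for continuous data". Section 10.4.3, on secondary endpoints, adds only that "For all analyses, the standard assumptions of Gaussian residuals and quality of variance will be tested", with a log transformation if they fail and count models for days on oxygen. No section names a covariate, matching, stratification, weighting or an age-standardised score.

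Age is available in both arms. It is an entry criterion for treated children, and section 5.1 applies the same one to controls: "Data collected for the control arm will be obtained via retrospective chart review for patients meeting the following inclusion criteria". Its only stated use is in section 10.4.6: "Baseline descriptive statistics will include participant age and gender".

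**The concern.** Resting heart rate and respiratory rate generally fall over the first two years of life, so within a 0-to-24-month range some of the variation between children is simply age. A two-sample test on levels leaves that variation in the error term. Without randomisation, it also attributes any difference in age mix between the periods to treatment, which could create an apparent effect on these two endpoints or hide a real one.

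Nothing in the design balances age within the permitted range. Treated children need parental consent and clearance from their care team (section 5.4), and those who leave early are dropped (section 10.4.5). Controls drawn from charts pass no such filter, and the plan does not say how 114 of them are chosen from the year.

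**Working it through.** **The plan's own figure.** Sections 4.1 and 10.5 size the study on length of stay: mean 6.5 days, SD 3.5, a 20% decrease (1.3 days), type I error 0.05, power 0.80. Two-sided, n per arm = 2 × (1.960 + 0.842)² × 3.5² / 1.3² = 113.8, so 114 per arm and 228 in total. This reproduces the plan. The point below concerns the analysis method, and the sample size does not change.

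**Assumptions, none of them in the documents.** Ages are spread evenly over 0 to 24 months, and levels are compared.
- Heart rate: within-age SD 15 bpm, falling 0.5, 1.0 or 1.5 bpm per month of age.
- Respiratory rate: within-age SD 10 per minute, falling 0.3, 0.6 or 0.9 per month.

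**Formulas.**
- Age SD = 24/√12 = 6.93 months.
- Raw SD = √(within-age SD² + (slope × 6.93)²). For heart rate at 1.5 per month: √(225 + 108) = 18.2.
- Effective n = 114 × within-age SD² / raw SD². In the same case: 114 × 225/333 = 77.
- Difference detectable with 80% power = 2.80 × SD × √(2/114).
- False-positive rate: noncentral t with 226 df, shift = slope × age gap, no treatment effect.

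| Endpoint, fall per month | Raw SD | Effective n | Detectable difference | 1-month gap | 2-month gap |
|---|---|---|---|---|---|
| Heart rate, 0.5 | 15.4 | 108 | 5.71 | 5.7% | 7.8% |
| Heart rate, 1.0 | 16.5 | 94 | 6.13 | 7.4% | 14.9% |
| Heart rate, 1.5 | 18.2 | 77 | 6.77 | 9.5% | 23.5% |
| Respiratory rate, 0.3 | 10.2 | 109 | 3.79 | 5.6% | 7.3% |
| Respiratory rate, 0.6 | 10.8 | 97 | 4.02 | 7.0% | 13.2% |
| Respiratory rate, 0.9 | 11.8 | 82 | 4.37 | 8.9% | 20.9% |

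With age fully accounted for, the detectable differences would be 5.57 bpm and 3.71 per minute. With no systematic age gap the error rate stays at 5%, and the only cost is precision.

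**How large a gap chance can produce.** SE of the difference in mean age = 6.93 × √(2/114) = 0.92 months. A 2-month gap is then z = 2/0.92 = 2.18, two-sided p = 0.029. A gap of that size arises by chance in about 3% of trials, so the right-hand column needs a real shift between periods.

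**Shape of the fall, and the remedies.** These were simulated with 8,000 trials per setting: control ages 0 to 24 months, treated ages 0 to 20 (a 2-month gap in means), and an assumed within-child correlation of 0.5. If the same total fall is concentrated in the first months (exponential, scale 6 months), the t-test on levels rejects in 5.7%, 8.0% and 11.2% for heart rate and 5.6%, 7.1% and 9.6% for respiratory rate. Those figures apply when the oldest children are the ones missing; a gap at the young end, where a curved fall is steepest, would do more. Across all 12 settings:
- Change from first reading rejects in 4.6% to 5.3%.
- Regression on arm, age and age squared rejects in 4.5% to 5.6%.
- The same with first reading added rejects in 4.7% to 5.3%.
- When the true fall is curved, a straight-line age term rejects in 4.8% to 7.4%, which is why a curve is worth allowing.

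**The case against.** The strongest reply is that no section says levels are compared. The Protocol Summary speaks of a trend after treatments, and the Schedule of Events pairs an enrolment reading of each vital sign with readings once per shift. Both fit a within-child change, which removes the bias in the simulation above. It may remove the precision cost too: if the assumed correlation of 0.5 holds among children of the same age, the change in heart rate has SD 15 × √(2 × (1 − 0.5)) = 15, equal to the within-age SD. This stands, and it makes the concern conditional. It does not dispose of it, because no analysis section specifies a change or a time point, and section 4.2.2 refers to the readings themselves.

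A reader might infer that the two periods cover different seasons and so different ages. The documents do not support that. The planned study duration is 12 months and the control window opens 12 months before the start, so both can span a full year; only early completion of recruitment at about 114 would change this. Unit, age range and exclusions are the same in both arms, and no section points to an age shift. Age will be summarised by group, so a gap would be visible, although seeing it does not correct for it.

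It is also fair to say that non-adjustment affects every endpoint, the primary ones included, and that age is only one possible difference between the periods. Finally, section 1 defers analysis until a biostatistician joins and section 10.1 refers to a formal SAP. Neither supplies a covariate, but the first leaves time to add one.

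**Conclusion.** The point holds as a minor, conditional one on two secondary endpoints. The stated comparison ignores a measured variable that is likely to explain part of the outcome. If levels are compared, 114 per arm does the work of about 77 to 109, depending on assumed slopes and SDs; at the shallow end the loss is trivial (5.71 against 5.57 bpm). A real age gap would add false positives: about 5.6% to 9.5% at 1 month, and at 2 months about 5.6% to 11% with a curved fall or up to about 24% with the steepest straight-line fall.

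A reader might infer that these comparisons are biased, or that nearly a quarter would be falsely positive. Neither follows. The first needs both a comparison of levels and a real age gap, and the documents establish neither. The second also needs the steepest assumed slope, a straight-line fall and a 2-month gap together. Nothing here bears on the primary conclusions.

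**What to change.** In section 10.4.3, replace the two-sample test for heart rate and respiratory rate with a regression on arm and age in months, allowing a curve (age and age squared). Add the child's first reading on the unit, taken before the first study treatment in the treated arm, as a covariate where control charts supply it; this also fits the trend wording in the Protocol Summary. Report the unadjusted result alongside, and state that the adjustment removes age differences only.

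Name the time point in section 4.2.2. The choice is the sponsor's, but it should not depend on when the child goes home, because length of stay is a primary outcome that treatment may change.

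The cost is plan wording and one regression per endpoint. Age needs no new data, since it is checked for eligibility in both arms. The first reading does have a cost: section 7.3.2 records enrolment vital signs for treated children only, so control values must be extracted from charts. That the four-hourly charting in section 9 also applied in the control year is an assumption.
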